## **Specific Aims:**

**Specific Aim 1:** To assess the effect of PRP treatment of FAI symptoms compared to standard corticosteroid treatment.

Hypothesis 1: We hypothesize that compared to corticosteroids, patients with FAI that are treated with PRP will have (i) lower pain scores (ii) improved Hip Disability and Osteoarthritis Outcome Score (HOOS), Patient Reported Outcome Measurement Information System (PROMIS) Global Health Scale scores and (iii) increased hip stability scores as measured by BioDex stability station functional testing.

**Specific Aim 2:** To determine if PRP treatment of FAI reduces (i) radiographic and (ii) biochemical markers of joint inflammation and cartilage degradation.

Hypothesis 2: We hypothesize that compared to corticosteroids, patients with FAI that are treated with PRP will have (i) a diminished change in Kellgren-Lawrence radiographic scores and (ii) reduced levels of circulating biomarkers C-reactive protein, cartilage oligomeric matrix protein and type II collagen propeptide levels in circulation.

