# **Primary Outcome:**

• Pain as measured by Visual Analog Scale (VAS)

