## **Secondary Outcome(s):**

- Patient reported function and symptoms
- Evaluate performance of serum biomarkers
- Change in Kellgren-Lawrence classification scores calculated from anterior-posterior (AP) pelvis radiographs between pre-treatment and 1 year post-treatment

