#### Plan for measurement of these outcomes:

- The Primary outcome measures will be:
  - o Change in 7 point pain Visual Analogue Scale (VAS)
- Secondary outcome measures include:
  - Hip Disability and Osteoarthritis Outcome Score (HOOS)
    - Western Ontario and McMaster Universities Arthritis Index (WOMAC), calculated as a subscore of the HOOS
  - Patient Reported Outcome Measurement Information System (PROMIS) Global Health Scale
  - o Serum Biomarker analysis: IFN-g, IL-6, MCP-1, MIP-1b, IL-1b, TNF-alpha, high-sensitivity CRP, COMP
  - Change in Kellgren-Lawrence classification scores calculated from AP pelvis radiographs between pre-treatment and 1 year post-treatment

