#### **Data Analysis:**

The study sample size is based upon power calculations for change in pain score data from a previous study by our group in patients with FAI. To detect a difference in the change in pain between the first and last visit of 1.7 units, on a 7-point pain scale, using a power of 80% and  $\alpha$ =0.05, requires at total N of 32, or 16 per group. To account for 20% of patients who might withdraw, we will recruit 8 additional subjects for a total of 40 patients. We will use a mixed-effects linear regression model to look at the changes in individual parameters at multiple time points over the course of the study, as well as the associations between changes of multiple parameters. Independent variables in the model are treatment assignment and time, dependent

variables are outcomes scores, biomarkers and Kellgren-Lawrence scores. First, we will perform univariate and univariable models to explore the relative importance of each predictor variable followed by a stepwise procedure in which we will include all significant variables in multivariable model followed by dropping the highest non-significant variable (significance will be set at p=0.10) until only significant variables remain. This will be repeated for each dependent variable. The robustness will be tested by performing model fitting and examining residual plots.

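### All eight serum markers go through the same stepwise procedure, with nothing separating the two hypothesised ones (CRP, COMP) from the other six and no control of error across them

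*Combined protocol and SAP*

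**What the plan says.** Under Specific Aims, Hypothesis 2(ii) predicts that PRP patients will have "reduced levels of circulating biomarkers C-reactive protein, cartilage oligomeric matrix protein and type II collagen propeptide levels in circulation". That is three markers.

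Plan for measurement of these outcomes lists eight: "Serum Biomarker analysis: IFN-g, IL-6, MCP-1, MIP-1b, IL-1b, TNF-alpha, high-sensitivity CRP, COMP". Summary of Human Subject Involvement and Follow-up Visits repeat the same eight, and Data Collection gives an assay for each. Two of the eight, hsCRP and COMP, are in the hypothesis. The other six are in no hypothesis, and the propeptide is on none of the measured lists.

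Under Secondary Outcome(s) the biomarker entry reads only "Evaluate performance of serum biomarkers".

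Data Analysis names two independent variables, treatment assignment and time. It says the dependent "variables are outcomes scores, biomarkers and Kellgren-Lawrence scores", with no distinction between markers. Variables that are significant in single-variable models enter a multivariable model, and the least significant are then dropped; "significance will be set at p=0.10". The section adds: "This will be repeated for each dependent variable". No section names a key marker, an order of testing, a multiplicity adjustment, a success criterion for Aim 2(ii) or an exploratory label.

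**The concern.** Aim 2 is worded broadly, as a reduction in biochemical markers of joint inflammation and cartilage degradation. Hypothesis 2(ii) is narrower, but nothing in the analysis ties the aim to it. A low p-value on any of the eight markers could therefore be offered as support for the aim, including on the six that nobody predicted would change.

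The stepwise rule adds to this. Treatment is one of only two named independent variables, so it is itself kept or dropped at p=0.10, and if kept it counts as significant in the plan's own terms. If it is dropped, the between-arm difference for that marker is not estimated in the final model.

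At stake is the credibility of the biomarker conclusion in a trial planned on 16 evaluable patients per arm. Future Directions says that elevated cytokines found here could support interest in targeted inhibitors. The cytokines are the unhypothesised markers.

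**Working it through.** **The plan's own figure.** Data Analysis gives a difference of 1.7 units, 80% power, α=0.05 and 16 per group, with 20% withdrawal.
- Withdrawal: 32 / (1 − 0.20) = 40, which reproduces.
- The 16 per group cannot be reproduced independently, because no SD is stated. With a two-sided t-test (assumed), 16 per group and 80% power imply a standardised effect d of 1.02, so SD = 1.7 / 1.024 = 1.66. The normal approximation gives 1.7 / [(1.960 + 0.842) × √(2/16)] = 1.72.
- The plan gives no power or error rate for any biomarker.

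**Inputs for the biomarker check.** Eight markers measured, two of them hypothesised (sections cited above). There are two candidate levels: 0.05, from the sample-size sentence, and 0.10, from the stepwise rule. I take one two-sided treatment test per marker and no true effect. Correlation between markers is not given, so a range is assumed.

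**Independent markers.** P(at least one false positive among m) = 1 − (1 − α)^m.

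| Markers | α = 0.05 | α = 0.10 |
|---|---|---|
| All 8 | 1 − 0.95^8 = 33.7% | 1 − 0.90^8 = 57.0% |
| The 6 unhypothesised | 1 − 0.95^6 = 26.5% | 1 − 0.90^6 = 46.9% |
| hsCRP and COMP only | 1 − 0.95^2 = 9.75% | 1 − 0.90^2 = 19.0% |

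**Correlated markers.** Simulation of eight equally correlated normal test statistics, 300,000 draws; chance of at least one false positive among the eight:

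| Assumed correlation | α = 0.05 | α = 0.10 |
|---|---|---|
| 0.3 | 30.0% | 51.3% |
| 0.5 | 24.9% | 43.6% |
| 0.7 | 19.0% | 33.6% |
| 0.9 | 11.9% | 21.6% |

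**After the proposed change.** Holm across hsCRP and COMP holds the family error at or below 5% whatever the correlation. Testing each at 0.025 gives 1 − 0.975^2 = 4.9% if they are independent.

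**Power cost.** At d = 1.02 and 16 per group, power is 80% at 0.05, 70% at 0.025 (first Holm step for two markers) and 49% at 0.05/8 = 0.00625 (first step for all eight).

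**The case against.** The strongest defence is that the biomarkers are secondary in a 40-patient trial that describes itself as the first of several. Hypothesis 2(ii) names its markers, so a result on IFN-g, say, would not confirm it as written. Both statements are correct. They keep the point away from the primary pain result, but they do not supply the missing rule: the analysis treats the named and unnamed markers identically, and the aim is broad enough to take in either.

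Four stronger readings are tempting, and the documents do not support them.
- A reader might infer a test at each of the four follow-up visits, and so 8 × 4 = 32 tests. Data Analysis describes a mixed model over time for each dependent variable and does not prescribe tests by visit. The figures above do not use visits.
- A reader might take 57% as the plan's error rate. The p=0.10 is written as a retention threshold, and 0.05 appears only in the sample-size sentence, so no explicit level for a biomarker claim is stated. Both columns are needed.
- A reader might conclude that the plan commits to acting on a chance cytokine result. Future Directions speaks only of what such a finding could support.
- A reader might suppose that the six other markers lose confirmatory standing under the fix. No section gives them that standing.

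It is also fair to object that correlation lowers the inflation. It does, but at 0.9 the chance is still about 12%, more than twice 5%.

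**Conclusion.** The concern holds for the secondary biomarker aim. Followed literally, the plan gives a 12% to 34% chance of at least one false marker effect at 0.05, and 22% to 57% if the retention threshold is used as the test level. The ranges run from an assumed correlation of 0.9 down to independence. They assume no true effect on any marker and a single treatment test per marker. The cause is the stated procedure together with the absence of any rule separating hypothesised from exploratory markers. The primary pain conclusion is untouched, so this is a correction that should be made rather than a flaw that undermines the trial.

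**What to change.** For Aim 2(ii), the Data Analysis section should say the following.
- The mixed model for each marker contains treatment, time and their interaction, with no stepwise selection, so that the between-arm contrast is always estimated.
- The aim is tested on hsCRP and COMP only, as the between-arm difference in change from baseline to the last visit, at two-sided 5% with Holm across the two. First-to-last change is the contrast the plan already uses to size the trial for pain.
- The other six markers, and the earlier visits for all markers, are exploratory: estimates and confidence intervals, with no claim of significance.

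Specific Aims must also be reconciled with the measured lists on type II collagen propeptide, which is hypothesised but not measured. If it is added to the assays, the Holm family becomes three and its first step 0.05/3 = 0.0167. If it is not, the hypothesis should be amended.

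The change to the tests needs no new samples, visits or patients; adding a propeptide assay would be extra laboratory work. The cost is power: for one marker at the first Holm step it falls from 80% to about 70% at a standardised effect of 1.02 SD. That effect is an assumption, back-solved from 16 per group, 80% power and two-sided 0.05; the documents state no effect size for any biomarker. A step-down procedure over all eight markers would also control the error, but at the same assumed effect its first step has about 49% power.

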# **Potential Pitfalls and Limitations:**

The study team has extensive experience studying FAI in patients in our MedSport clinic at the University of Michigan. All techniques and methodologies are currently in use and have previously been published in top orthopaedic journals. The main limitation we perceive is recruiting a sufficient number of subjects to the study. However, we have a high volume of patients pursuing treatment for FAI and anticipate it would be easy to recruit subjects into the study. While we think that a mixed-effects linear regression model is appropriate and informative for this study, an alternative approach would be a two-way repeat measures ANOVA. Given the statistical expertise of the study team, we do not anticipate any problems in performing analyses.

## **Future Directions:**

We hope this study is the first of several evaluating the use of PRP in the treatment of FAI. If the results from this study are promising, larger multicenter studies and extended time points would be warranted. Identifying specific pro-inflammatory or pro-atrophy cytokines which are elevated could also support the potential use of targeted inhibitors of these factors to reduce inflammation and improve strength.

